Falls remain the leading cause of injury, long-term disability, premature institutionalization, and injury-related mortality among older adults and are projected to cost nearly \$59.7 billion by 2020.^{12-15, 71} Fall-related mortality increases with age.⁷² Although numerous clinical interventions have demonstrated efficacy in reducing the incidence of falls,⁷³ translation to the community has failed; fall rates continue to escalate. Indeed, nearly one third of all adults older than 65 years fall each year. The majority of falls experienced by older adults, particularly more frail high risk older adults, occur in the home,^{12, 24, 25} and measurable home hazards are associated with an increased risk of older persons falling in the United States.^{74,26}

Setting. This intervention will be implemented and evaluated in the urban core of St. Louis, Missouri, an area of high need for an effective fall prevention program. In Missouri, the fall death rate for older adults is consistently higher than the national average. The rate nearly doubled between 2000 and 2009 from 38 to 72.32 per 100,000.⁷⁵ Falls are the leading cause of unintentional injury-related hospitalizations and ED visits among older Missourians; older adults account for 64% of all ED visits and hospitalizations resulting from falls, which is higher than national rates.^{76, 77}

Our long-term goal is to improve older adults' ability to maintain their independence and safety in the community by translating fall prevention research into effective community programs. We plan to establish the effectiveness of a program that demonstrated a reduction in falls among community-dwelling older adults at high risk for a fall. It is a practical and scalable intervention recommended by the Centers for Disease Control and Prevention(CDC).¹ The intervention will be delivered by OTs in an Area Agency on Aging (AAA)—part of the Aging Services Network⁵³ in the US. We will use community-engaged research approaches⁵⁴ and a hybrid design⁵⁵ to study both the effect of the intervention in a real world setting *and* the implementation strategy. We will prepare for dissemination⁵⁶ by providing cost estimates, fidelity metrics, and intervention manuals.

Design of study:

To examine the effect of a home modification (home hazard removal) program, we will conduct a hybrid effectiveness/implementation trial of 300 older adults at risk for a fall randomized to a home hazard removal program or usual care, and follow them for 12 months. We will conduct a pragmatic randomized controlled trial/implementation study

Recruitment: We will recruit participants through the SLAAA's annual assessment of participant's health. .

Deliver intervention: Interventionists will use a manualized protocol to deliver the intervention.

Follow up: We will follow participants monthly using a highly successful calendar journal technique that has demonstrated a 99% response rate in previous studies.

Dissemination: We will disseminate the program, manuals and training programs using our advisory network.

Objectives of study:

1. Determine the acceptability costs and feasibility of delivering the program in an Area Agency on Aging.

Agency on Aging. We will conduct a process evaluation⁷⁸ of the intervention to aid in dissemination and interpretability of the trial by evaluating acceptability, feasibility, safety, and cost. **We will test the hypothesis** that home modification interventions will have high acceptability (80% retention), high fidelity by therapists (95% of elements; 90% of dose delivered), low safety risk (no increased rate of falls compared to usual care group), and high adherence (80% of modifications in use) at 12 months.

2. Determine if the program is effective in reducing the rate and risk of falls and improving the outcome of other participant-reported outcomes (PROs) that can be effected by the intervention. **We will test the hypothesis** that older adults who receive the program will have a lower rate and risk of falls, improved self-efficacy, daily activity performance, and quality of life compared with the usual care group.

Expected outcomes: The central hypothesis of this study is that home modifications (home hazard removal) will be acceptable to older adults, practical for delivery in an existing social service network, and efficacious in reducing falls and maintaining independence for older adults. Our research team has a unique skill set to address this problem, including: a long relationship with an AAA, experience studying home modifications in the community, experience conducting pragmatic trials, and expertise in dissemination and implementation science. If successful, this study could have immediate positive impact by leading to dissemination and implementation of a program with high adherence, structured to deploy within an existing aging services network that could significantly reduce falls among community-dwelling older adults at high risk.

2 STUDY OBJECTIVES

2.1 Primary Objective

Determine the acceptability and feasibility of delivering the program in an AAA. To examine the effect of the adapted program, we will conduct a hybrid effectiveness/implementation trial of 300 older adults at high risk for a fall who will be randomized to the adapted program or usual agency care and then followed for 12 months. We will conduct a process evaluation⁷⁸ of the intervention to aid in dissemination and interpretability of the trial by evaluating acceptability, feasibility, safety, and cost. We will test the hypothesis that home-modification interventions will have high acceptability (80% retention), high fidelity by therapists (95% of elements; 90% of dose delivered), low safety risk (no increased rate of falls compared with the usual care group), and high adherence (80% of modifications in use) at 12 months.

2.2 Secondary Objectives

Determine whether the adapted program is effective in reducing the rate and risk of falls and improving the outcome of other participant-reported outcomes that can be affected by the intervention. We will test the hypothesis that older adults who receive the program will have a lower rate and risk of falls and improved self-efficacy, daily-activity performance, and quality of life compared with the usual care group.

If successful, this study could have immediate positive impact by leading to dissemination and implementation of a program with high adherence that is structured to deploy within an existing aging services network and that could significantly reduce falls among community-dwelling older adults at high risk.

3 BACKGROUND AND RATIONALE

3.1 Background on Condition, Disease, or Other Primary Study Focus

Falls remain the leading cause of injury, long-term disability, premature institutionalization, and injury-related mortality in the older adult population.¹²⁻¹⁵ Falls are the most common cause of traumatic brain injury and fracture for older adults,¹⁶ and they have serious complications such as institutionalization,¹⁷ functional dependence, and paralyzing fear of falling.^{18, 19} Every 29 seconds, an older adult dies from the consequences of a fall.²⁰ Falls are an eminent threat to a frail, older adult's ability to maintain independence in the community. Approximately 1 in 3 community-dwelling adults aged 65 years and older fall each year,^{21, 22} and those older than age 70 have an especially high fall risk.¹⁴ Older adults who have experienced a previous fall are at a greater risk of falling again.²³ Prevalence of the home hazard condition: *The majority of falls experienced by older adults, particularly more frail, high-risk older adults, occur in the home,^{12, 24, 25} and measurable home hazards are associated with an increased risk of older persons falling*

*in the US.*²⁶ Economic impact: Falls are costly: \$30 billion a year is spent treating older adults for the effects of falls.²⁷ As the population ages, costs associated with falls are projected to reach \$59.6 billion by 2020,²² making fall prevention a public health priority. Gap addressed by this proposal: Efficacy studies conducted in Australia and Europe and results from our own efficacy trial suggest that home-modification delivered by OTs can significantly reduce falls among community-dwelling older adults at high risk.²⁸ Despite these findings and recommendations from the American Geriatrics Society that home modifications be routine for community-dwelling older adults at high risk for a fall,²⁹ home-modification implementation is not standard practice in the US. New models of care must be developed to effectively implement this strategy nationally. We plan to address this gap by implementing and testing the effectiveness of a home-hazard removal program in the US Aging Services Network. This study will be based on our recently completed home-modification trial in the US.

Home modifications to improve daily-activity performance have been studied in the US,^{5, 50} and there is promising preliminary evidence of the *efficacy* of home-hazard removal to reduce the risk of falls (including our unpublished trial). However, no evidence shows the pragmatic *effectiveness* of home modifications to prevent falls in the US. Important next steps to advance the science include better understanding of the effectiveness and implementation of home-hazard removal.

3.2 Study Rationale

Fall prevention programs, despite success in clinical trials, have not translated to a reduction in falls for community-dwelling older adults in the US. The most efficacious fall-prevention intervention identified to date is **exercise**. In randomized controlled trials, multicomponent exercise groups and individually prescribed exercises have been shown to reduce the rate and risk of falls³⁰. Although effective in controlled studies,^{31, 32} adherence rates in community programs are low (29%–59%),³³⁻³⁵ and older adults report a reluctance to initiate exercise programs to reduce their chance of falling.^{36, 37} This finding is not surprising, given the low rate of participation in fitness activities among older adults in general, despite aggressive public health campaigns to increase physical activity.³⁸ Additional intervention strategies with high acceptance are needed to address the important public health problem of falls.

Home-modification interventions, when delivered by OTs, *also demonstrate efficacy in reducing falls*³⁰ among high-risk populations.²⁸ Home modifications can include installation of stairway railings, grab bars, slip-resistant surfacing in the bathroom, and provision of lighting. Home-hazard removal is strongly recommended by the American and British Geriatric Societies to prevent falls.²⁹ Indeed, home modification interventions, *when delivered by OTs*, have been shown to reduce falls by 39% among high-risk fallers³⁹⁻⁴¹ in studies conducted in Europe and Australia.

Fall-prevention interventions have not been effectively translated into prevention programs. This study will be a substantial departure from previous studies. The research proposed in this application is innovative, in our opinion, because it represents the first time an effective home-modification intervention to prevent falls will be implemented through a US social service delivery system. Successful translation into practice requires an understanding of the interaction among an intervention, the systems in which it is implemented, and the stakeholders.⁴² We will use community-engaged research approaches⁴³⁻⁴⁶ to determine adaptations necessary to deploy a home-modification intervention to prevent falls in the US within a reliable aging services network. We will reduce barriers to program participation by involving key stakeholders as part of the research team^{47, 48} and clarifying the benefits of the research to the community.⁴⁹

The goal of this study is to implement an evidence-based home-modification intervention for older adults that is designed to reduce the incidence of falls through a community program delivered through the aging services network with high acceptance. The program will be designed to reduce the incidence of falls among community-dwelling older adults so they may independently remain in their own homes as long as possible.

4 STUDY DESIGN

To examine the effect of a home-modification (home-hazard removal) program, we will conduct a hybrid effectiveness/implementation trial of 300 older adults at risk for a fall who will be randomized to a home-hazard removal program or usual care and then followed for 12 months. Figure 5 outlines the milestones of a pragmatic randomized controlled trial and implementation study. Study milestones are further detailed in the timeline (under Section E.1, Table 2).

Recruitment: We will recruit participants through the SLAAA's annual assessment of participants' health. We estimate more than 800 older adults will meet eligibility criteria.

Deliver intervention: Interventionists will use a manualized protocol to deliver the intervention.

Follow-up: We will follow participants monthly using a highly successful calendar journal

technique that has demonstrated a 99% response rate in previous studies. Dissemination: We will disseminate the program, manuals, and training programs using our advisory network.

Pragmatic trial designed for implementation and dissemination

300 community-dwelling older adults with high risk of fall
-Baseline assessment
-Randomization

Intervention (150)
Home hazard removal

Control (150)
usual care

12 month follow-up

12 month follow-up

4.1 Timeline and Tasks

Resource	Staff	Month							
		-3-0	1-6	6-12	13-18	19-24	25-30	31-36	
Personnel									
Weekly lab meetings	SS	XX	XXX	XXX	XXX	XXX	XXX	XXX	XXX
Advisory board meetings	SS	X	▪ ▪	▪ ▪	▪ ▪	▪ ▪	▪ ▪	▪ ▪	▪ ▪
Staff training	SS	X							
Human Subjects									
HRPO approval/renewal	JC	X		▪		▪			▪
Quality Assurance Plan									
development	SS	X							
oversight	WU		▪	▪	▪	▪	▪	▪	▪
Report to advisory committee	SS		▪	▪	▪	▪	▪	▪	▪
Study Tasks									
Manuals & training materials	SS		XXX						
Recruit, enroll participants	JC		XXX	XXX	XXX				
Baseline assessment	ES		XXX	XXX	XXX				
Deliver intervention	ES			XXX	XXX	XXX	XXX		
Follow-up	JC			XXX	XXX	XXX	XXX	XX	
Data management and analysis									
Database	LH	XXX	XXX	XXX	XXX	XXX	XXX	XXX	XXX
Conduct interim analyses	YY			X	X	X	X	X	X
Conduct final analyses	YY								XXX
Dissemination and Implementation									
Meeting with participants and community	SS								▪
Dissemination planning meeting	SS	▪		▪		▪			▪
Peer-reviewed publications									
Protocol	SS		▪						
Implementation outcomes	SS								▪
Intervention outcomes	SS								▪

Note: x = 2 months; ▪ = single event; SS=[name]; JC = [name]; WU = oversight; ES = [name]; LH = [name]; YY = [name]

5 SELECTION AND ENROLLMENT OF PARTICIPANTS

5.1 Inclusion/Exclusion Criteria

Inclusion criteria: 1) aged 65 years or older; 2) self-report of one previous fall or more in the preceding 12 months or self-report as “worried about falling;” and currently receiving services from SLAAA.

Exclusion criteria: 1) residents of nursing homes; 2) individuals with severe cognitive impairment who are unable to give consent to participate (as determined by a score of greater than 10 on the SBT for memory¹⁰)

5.2 Study Enrollment Procedures

Study population, eligibility, and screening. The National Aging Program Information System (NAPIS) is a database of information collected annually by the AoA from state units on aging describing the general health, nutritional, financial, functional, and environmental status of an older adult. Missouri’s assessment (MA4) currently *includes an evidence-based fall-risk screening* as part of an extensive battery of standardized assessments. In the current cohort of 1,331 older adults screened in CY 2013 by SLAAA, the average age of the cohort is 77 years, 67 percent are female and 74% are African American. More than 25% reported a fall in the past 12 months, and 40% are “worried about falling.” The average score on ADL performance was 4 (range, 1–7); indicating moderate ADL impairment). We will recruit from this cohort of older adults who are “at high risk for a fall.”⁷⁹ We estimate more than 800 older adults will meet eligibility criteria in the cohort. ^{2,3} The SLAAA staff will identify potential participants and assist in recruiting participants at no cost

We will recruit 300 older adults, conduct baseline assessments, and randomize participants to receive the adapted program or usual care. Outcomes (falls, fall self-efficacy) will be assessed by a blinded evaluator at baseline and 12 months after intervention. Flow through the study is illustrated in Figure 5. All assessments and study visits will occur in participants’ homes.

Recruitment. We will randomly select a sample of older adults from the large observational cohort of older adults assessed annually by SLAAA via NAPIS as part of service delivery⁸⁰ and invite them to participate by telephone. Refusals will be tracked for attribution of cause.

Consent and enrollment. Consent will be obtained at the baseline home assessment visit. Potential participants will be provided with a study brochure and a copy of the large-print consent form. Scripted details of the project including the randomization procedure, study interventions, and follow-up procedures will be discussed (under Section C.2.c).

Randomization sequence generation, allocation concealment, and implementation.

Participants will be allocated using a 1:1 ratio via randomization sequences generated a priori using a computerized formal probability model. The allocation ratio will be maintained at periodic intervals. Groups will be balanced with regard to race (self-reported African American

or “other”) and sex. Randomization sequence concealment will be achieved by the Research Electronic Data Capture (REDCap) system.⁸¹ After baseline assessment, the study coordinator will verify that all eligibility requirements are satisfied and then elicit treatment assignment.

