7 STUDY PROCEDURES

7.1 Schedule of Evaluations

7.2 Overview

Assessments will be conducted at baseline and 6 months after intervention for participants in the treatment group and will occur in participants' homes. For those in the control group, no 6 month assessment will occur. A 12 month phone follow up will occur for all participants.

Treatment

Control

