7.3.3.5 Raters

Follow up assessments will be conducted by trained raters blind to group allocation. The follow-up sessions will repeat assessments conducted at the first study home visit and first phone call.

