7.4.6 Cost

The cost of the treatment will be measured by tracking cost of modifications and adaptive equipment for each participant. This will be tracked using the Invoice Form which includes both

costs from the contractor as well as costs of any equipment ordered from a medical supply company or obtained from a community resource (medical equipment lending program). The total amount of money spent on each person will be tracked on this form.

7.5 Overview of study assessments by time point.

	Phone Screening	Consent visit	Baseline assessment	Treatment session (tx group only)	Follow-up months 1-12	5 month phone call (tx group only)	6 month Booster in home (tx group only)	12 month phone call
Consent		x						
Calendar Questionnaire		x						
Demographics		x						
WeHSA			x	x			x	
SMAST-G			x					
GDS		x						
SBT	x							
Medication		x						
ROM			x					
Strength			x					
Grip Strength			x					
Near Visual Acuity			x					
Contrast Sensitivity			x					
POMA			x					
Falls			x	x	x			x
OARS			x					x
FES		x						x
PROMIS		x						x
Falls behavioral Scale		x						x
Fidelity to treatment (visit by visit grid)			x	x			x	
Time (Dose), Completion of Session, Cost				x			x	
Adherence						x	x	x

*randomization before T1

*both groups will send in monthly fall journal information

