
11 DATA COLLECTION AND QUALITY ASSURANCE

11.1 Data Collection Forms

Data will be collected at each follow up point by a blinded rater over the phone. Data will be directly entered into an online data management software (see 11.2) Back up paper forms will be available (See MOP).

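### Section 5.2 puts the blinded 12-month assessment in the participant's home, while Sections 7.2, 7.5 and 11.1 make it a phone call; one mode should be fixed, and the rater kept from learning the arm

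*Combined protocol and SAP*

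**What the plan says.** Section 5.2 (Study Enrollment Procedures) states that "Outcomes (falls, fall self-efficacy) will be assessed by a blinded evaluator at baseline and 12 months after intervention". Two sentences later, in the same paragraph, it adds: "All assessments and study visits will occur in" participants' homes. No exception is made for month 12.

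Three other places specify telephone:
- Section 7.2: "A 12 month phone follow up will occur for all participants".
- The Section 7.5 table: the last column is headed "12 month phone call". It ticks Falls, OARS, FES, PROMIS, the Falls behavioral Scale (FaB) and Adherence.
- Section 11.1: "Data will be collected at each follow up point by a blinded rater over the phone".

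Two places lean towards an in-person assessment without stating a mode. Section 7.3.3.5 first says "Follow up assessments will be conducted by trained raters blind to group allocation", and then "The follow-up sessions will repeat assessments conducted at the first study home visit and first phone call". Section 7.3.4 introduces its list of closing assessments as belonging to a final visit.

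**The concern.** The intervention changes the home. Section 3.2 gives stairway railings, grab bars, slip-resistant bathroom surfacing and lighting as examples, and Section 7.3.3.1 has the occupational therapist install equipment such as a tub transfer bench. A rater who goes into the home at 12 months may see these things. A rater on the telephone will not. The mode of the 12-month assessment therefore bears directly on whether the blinding claimed in Sections 5.2, 7.3.3.5 and 11.1 can hold.

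At stake are the 12-month ratings of fall self-efficacy, daily activity and global health, which Section 10.3 compares between arms. Staff working from Section 5.2 would run that assessment differently from staff working from Sections 7.2, 7.5 and 11.1.

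**Working it through.** No sample size, power or error rate is involved, so there is nothing to compute. The check sets side by side every place that bears on the mode or blinding of the 12-month assessment.

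| Place | Mode at 12 months | Blinding |
|---|---|---|
| Section 5.2, Study Enrollment Procedures | Home, no exception | Blinded evaluator |
| Section 7.2, Overview | Telephone, all participants | Not stated |
| Section 7.3.3.5, Raters | Not stated; repeats assessments from the first home visit and first phone call | Blinded raters |
| Section 7.3.4, Final evaluation | Called a visit | Not stated |
| Section 7.5, table | Telephone | Not stated |
| Section 11.1, Data Collection Forms | Telephone, every follow-up point | Blinded rater |

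**Mode.** One place says home, three say telephone, and two lean towards in-person contact. No text ranks them.

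**Content.** Sections 5.2 and 7.3.2.1 place consent at the first, baseline home assessment visit. Baseline includes the WeHSA hazard inspection, POMA, grip strength and contrast sensitivity. Read literally, Section 7.3.3.5 would have blinded raters repeat these, including an inspection of the very hazards that the intervention removes. The 7.5 table ticks none of them at 12 months. Section 7.3.4, by contrast, lists FaB, OARS, FES-I and PROMIS, the same four scales as the table, so there only the reference to a visit conflicts.

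**What a visiting rater could learn.** The cues in Sections 3.2 and 7.3.3.1 are visible, so the arm could often be inferred. It could not always be:
- removing a throw rug or giving self-management training, both in Section 7.3.3.1, leaves nothing to see;
- control participants may receive service referrals under Section 6.1;
- adaptive equipment already in use is recorded at baseline under Section 7.3.2.3.

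**Which outcomes are exposed.** Time to first fall, the primary outcome in Section 10.3, rests on the process in Section 7.3.3.4: daily journals mailed monthly and verified by a coordinator by telephone. That process does not depend on where the 12-month assessment takes place, although the coordinator's own blinding is not stated. What remains is FES-I, OARS, PROMIS and FaB. The first three match secondary outcomes in Section 10.3; FaB is collected but not named there.

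**Does telephone alone protect the blind?** No. The 7.5 table also ticks Adherence at the 12-month call. Adherence is the share of recommended modifications in use, and Section 10.3 estimates it in the intervention group only. A rater who has to ask about it learns the arm.

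**The case against.** The strongest reply is that the operative sections already agree. The overview, the schedule and the data-collection section all say telephone. Section 5.2 is an enrollment section whose sentence may have been meant for baseline, and the opening line of Section 7.3.4 reads like leftover template text. On that view this is an editing slip that staff following the schedule would never act on. Much of this stands, and it is why the point is minor. It does not remove the conflict: the 5.2 paragraph itself names the 12-month assessment before placing all assessments in the home, and Section 7.3.3.5 points the same way.

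A second reply is that participants know whether a therapist came to their home and that they answer these scales themselves, so an unblinded rater only adds to a bias that telephone contact leaves in place. That is correct and limits the gain. It does not justify adding rater knowledge as a second source of bias.

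A reader might also be tempted by four stronger readings that the documents do not support:
- *Nearly every intervention home would unmask the rater.* The 80% adherence target in Section 2.1 is a share of modifications, not of homes, and not every modification is visible.
- *The primary result is at risk.* The journal process does not depend on the mode of the 12-month assessment.
- *The arms would be assessed by a mix of home and telephone.* No section plans that at 12 months.
- *The 6-month in-home assessment in Section 7.2, held only in the treatment arm, is a blinded assessment that cannot be blind.* Section 7.2 does not call it blinded. Sections 6.1 and 7.3.3.3 and the 7.5 table show it to be the therapist's booster visit, with none of the four outcome scales ticked. Only its label needs correcting.

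**Conclusion.** The contradiction is real, stands in current text and is not resolved anywhere in the documents. Followed as written, Section 5.2 would send a supposedly blinded rater into homes where the arm can often be guessed. The possible harm is confined mainly to the secondary 12-month ratings, and no number can be put on it because the documents do not say how many homes would carry recognisable modifications.

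The conclusion rests on one inference that the protocol never states: that visible modifications tell a visitor the arm. That is likely in many homes and certain in none. Severity is low, and confidence in any material effect on the results is limited. The change is still worth making, because it protects a blinding claim on which the secondary comparisons rely, and because the Adherence item could defeat that claim even by telephone.

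**What to change.** 1. **Section 5.2.** Replace the blanket sentence with text such as: *Consent, baseline and treatment visits take place in the home. The 12-month outcome assessment is by telephone in both arms, by a rater blind to allocation who has made no visit to the home after randomisation.* Sections 5.2 and 7.3.2.2 disagree on whether randomisation follows or precedes baseline. If it precedes baseline, this rule would also exclude whoever did the baseline visit, so settle the order first.
2. **Sections 7.3.3.5 and 7.3.4.** Limit both to the items ticked at 12 months in the 7.5 table, and call the contact a telephone assessment rather than a visit.
3. **Section 7.2.** Label the 6-month treatment-arm contact as the occupational therapist's booster, not a blinded assessment. Word Section 11.1 so that it does not cover that contact.
4. **Adherence at 12 months (treatment arm).** Have a different, unblinded staff member collect it, or have it asked only after the outcome scales are completed and locked.

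The cost is protocol wording plus a small constraint on who makes the 12-month call or in what order the items are asked. A 12-month call to all participants is already in the schedule.

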Enrollment. Enrollment is defined as the date all of the screening criteria are met and the individual agrees to participate. The enrollment date will be recorded on a case report form.

7.3.2.2 Randomization.

Participants will be allocated using a 1:1 ratio via randomization sequences generated a priori using a computerized formal probability model. The allocation ratio will be maintained at periodic intervals. Groups will be balanced with regard to race (self-reported African American or “other”) and sex. Randomization sequence concealment will be achieved by the Research Electronic Data Capture (REDCap) system.⁸¹ The study coordinator will verify that all eligibility requirements are satisfied and then elicit treatment assignment prior to baseline assessment.

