7.3.3 Intervention and follow up sessions

7.3.3.1 Intervention

Participants randomized to the intervention group will receive the intervention over 2 visits and one booster session at 6 months according to a manualized intervention. Briefly, for the intervention group, the occupational therapist will begin the intervention during the WeHSA. During the WeHSA the occupational therapist will assist the older adult to identify home hazards, work through potential solutions to reduce or remove the hazard, if possible, implement solutions (such as removing a throw rug), create plan for additional hazard removal, begin self-management training for behavioral and environmental fall risks, and provide training to complete the calendar journal. Between visits, the occupational therapist will assist the older adult to obtain equipment or home modifications. At the second visit, the occupational therapist will provide any necessary installation of equipment (such as a tub transfer bench), explain the purpose of each new equipment, teach techniques to safely use the equipment, and observe the older adult safely using the equipment. The occupational therapist will also continue the self-management training to improve daily activity performance and safety.

7.3.3.2 5 month adherence

A phone call to evaluate adherence will be made at approximately five months (in anticipation of the 6 month booster session).

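### No rule covers two clients in the same home, although the intervention changes the dwelling, so a control who lives with an intervention participant would be partly exposed

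*Combined protocol and SAP*

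**What the plan says.** Sampling is of individuals. Section 5.2 states: "We will randomly select a sample of older adults from the large observational cohort of older adults assessed annually by SLAAA". Allocation is also individual. Sections 5.2 and 7.3.2.2 both state: "Participants will be allocated using a 1:1 ratio via randomization sequences generated a priori using a computerized formal probability model". The only balancing factors named are race and sex.

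Section 5.1 lists two exclusions: "Exclusion criteria: 1) residents of nursing homes; 2) individuals with severe cognitive impairment who are unable to give consent to participate". Neither concerns another participant in the same home. The screening and enrolment steps in sections 7.3.1 and 7.3.2 do not raise it either, and the assessment table in 7.5 has no co-residence item.

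The treatment is described largely as a change to the dwelling. Section 3.2 says: "Home modifications can include installation of stairway railings, grab bars, slip-resistant surfacing in the bathroom, and provision of lighting". Under section 7.3.3.1 the therapist removes hazards on the spot and later installs equipment. Sections 6.1 and 7.3.3.1 also describe components aimed at the person: a clinical assessment of functional limitations, self-management training, and teaching and observing the use of equipment.

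The sample size section (9.1, under heading 10) makes no allowance for contamination. The analysis section (10.3) has no household term.

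**The concern.** A rail, a lit stairway or a slip-resistant bathroom floor serves everyone who lives there. If spouses or siblings are both SLAAA clients and both qualify, nothing in the visible plan stops both from enrolling. With individual 1:1 allocation, about half of such pairs would be split. The control member would then live through follow-up in a modified home.

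This lowers fall risk in some controls and shrinks the contrast on time to first fall and on the other fall outcomes. It cannot be undone once the homes have been changed. Because co-residence is not listed among the data collected, its extent would also be hard to establish afterwards.

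**Working it through.** **Inputs from section 9.1.** Twelve-month fall-free proportions of 0.39 (control) and 0.58 (intervention), 150 per arm, 20% attrition, two-sided 0.05, stated power 84%, stated hazard ratio 0.5785.

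**Inputs from section 5.2.** A cohort of 1,331, more than 25% with a fall, 40% worried about falling, and more than 800 estimated eligible.

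**Assumed, because the documents give no figure.** q, the share of eligible clients who live with another eligible client, from 5% to 30%.

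**Step 1: reproduce the plan's figure.**
- HR = ln(0.58)/ln(0.39) = 0.5785, as stated.
- Analysed per arm = 150 × 0.8 = 120. Expected events = 120 × (0.61 + 0.42) = 123.6.
- Freedman log-rank power = Φ(√events × (1 − HR)/(1 + HR) − 1.96) = Φ(2.969 − 1.960) = 84.3%, which matches the stated 84%.

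**Step 2: share of controls exposed.** Draw 300 at random from E eligible people and allocate independently 1:1. A control's eligible housemate is then in the intervention arm with probability 150/(E − 1). For E = 800 this is 150/799 = 18.8%. So c = q × 150/(E − 1).

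**Step 3: effect on power.** Under full transfer of benefit, the control fall-free proportion becomes S0 = 0.39 + 0.19c. Then HR = ln(0.58)/ln(S0), events = 120 × (1 − S0 + 0.42), and the formula in step 1 applies. Half transfer replaces c by c/2.

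| E | q | c | HR, full | Power, full | Power, half |
|---|---|---|---|---|---|
| 800 | 5% | 0.9% | 0.581 | 83.7% | 84.0% |
| 800 | 10% | 1.9% | 0.584 | 83.0% | 83.7% |
| 800 | 20% | 3.8% | 0.590 | 81.5% | 83.0% |
| 800 | 30% | 5.6% | 0.596 | 80.0% | 82.3% |
| 532 | 30% | 8.5% | 0.604 | 77.6% | 81.2% |

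The 532 row takes 40% of 1,331, which is the pool if everyone who reported a fall is also in the worried group.

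**Step 4: number of pairs.** With E = 800 and q = 10% there are 800 × 0.10/2 = 40 co-resident pairs. Both members are drawn in 40 × (300/800) × (299/799) = 5.6 of them, and 5.6 × 150/299 = 2.8 are split. At q = 30% the same steps give 16.8 enrolled pairs and 8.4 split.

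**Step 5: couples who enrol together.** If the housemate of every co-resident participant also enrols, c = q × 150/299. At q = 20% this is 10.0%, which gives HR 0.609 and power 76.2% with full transfer.

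**The case against.** The best defence is that the problem is small under the plan's own sampling. A housemate matters only if he or she is an SLAAA client, is at risk, is among the 300 drawn and is allocated to intervention. For an eligible housemate in a pool of 800, the last two conditions together have a chance of about 19%. A trial with three to eight split pairs loses a few points of power at most, and the bias cannot create a false claim of benefit. This stands, and it sets the size of the point. It does not remove the gap.

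A reader might infer that a co-resident control simply receives the treatment. The documents do not support that. The functional assessment, the self-management training and the observed use of equipment are directed at the individual, and the physical changes are chosen for someone else's limitations. Full transfer of benefit is therefore an upper bound.

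A reader might also infer that shared homes invalidate the log-rank and Cox analyses, or that split households break the masking of the telephone raters. Neither carries much weight. Same-arm pairs inflate the variance of the treatment contrast and split pairs reduce it, so with individual 1:1 allocation the two largely offset, and few pairs are expected. Any intervention participant can reveal the allocation to a rater, so a handful of housemates adds little. Falls in any case come from participants' own daily calendars (7.3.3.4).

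Finally, an address check could sit in the manual of procedures that section 11.1 mentions, which was not available. The finding is that no rule is visible in the protocol text.

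**Conclusion.** The point holds as a design gap of modest expected size. The plan as written allows a control to live in a home modified for another participant, with bias toward no effect. With 800 eligible, random sampling and 5% to 30% co-residence, about 1% to 6% of controls would be exposed. Power would be 83.7% to 80.0% with full transfer and about 84.0% to 82.3% with half, against 84.3% reproduced. The co-residence range and the degree of transfer are assumptions.

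Power near 76% should not be read as the expected result. It needs 10% of controls exposed with full benefit, for example 20% co-residence with couples always enrolling together, and the documents give no support for that. A loss beyond the main range remains possible if the pool is smaller than estimated. Reaching 800 requires little overlap between the fall and worry groups: 25% plus 40% of 1,331 is 865 with no overlap. With full overlap and 30% co-residence, full-transfer power is 77.6%.

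The change is worth making because it is cheap before enrolment, while the exposure cannot be reversed later.

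**What to change.** Add to section 5.1 an exclusion such as: *another member of the same household is already enrolled in this trial*. Add to section 5.2 that addresses are checked before invitation and that, where several eligible clients share a home, one is selected at random. The documents do not say whether SLAAA records can be matched by address. If they cannot, ask about housemates at the screening call.

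The cost is one criterion and a short check, by the SLAAA staff who already identify candidates or by the coordinator who screens. A few co-resident clients could not join. The pool can bear this: with 800 eligible and 30% living in pairs, 800 × (1 − 0.30/2) = 680 households remain for 300 places. With 532 eligible, about 452 remain before refusals. The sample size stays at 300 and contamination from this source falls to zero. By comparison, restoring 84% power through enrolment alone would take about 306 to 336 participants over the main range, and the bias would remain.

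If the sponsor prefers not to exclude anyone, co-residents could be allocated together, with household recorded and a cluster-robust variance in the Cox model. That also prevents split homes, but it complicates the randomisation and the analysis.
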